STATISTICAL ANALYSIS PLAN FOR
“The Effect of Physician Ownership on Dialysis Outcomes”

PROTOCOL ID: HS-18-00530-1

SECONDARY ID: K08DK118213

Version #2

Last Modified: 3/11/2021

PI: [name], MS

Keck School of Medicine of the University of Southern California

ANALYTIC DATASETS

Facility level dataset

- 1) Merge the physician ownership dataset with DFC
 - a. Primarily use 2017 data, but if a facility is missing data, salvage with 2018, 2016, 2015 years
- 2) Merge zip codes with census / ACS characteristics
- 3) Merge with the facility survey (from 2017)
- 4) Restrict to free-standing facilities where $\leq 15\%$ of patients in 2017 were pediatric (< 18 years old)
- 5) Variables of interest
 - a. Facility Characteristics
 - i. Profit status
 - ii. Chain vs. independent
 - iii. Size of facility (Number of patients)
 - iv. Staff : patient ratio
 - v. ESRD Network
 - b. Outcomes
 - i. All quality measures from DFC dataset
- 6) Get distribution of patient characteristics for each facility
 - a. Link each facility to a patient
 - i. To assign a patient to a facility, first identify all dialysis patients with at least one month of dialysis in all of 2017 and meeting all of the following criteria
 1. Adults with valid 2728 form
 2. In the USA.
 3. Has Medicare FFS for that month of dialysis
 - ii. If a patient has multiple facilities, assign that patient to the facility that holds the plurality share
 - iii. If there are still ties in facilities, use the first observed facility that has the plurality
 - b. For each patient, for the first observed month of dialysis, get:
 - i. Age, Gender, Race, Ethnicity, Payer, Dual-Eligible (if Medicare)
 - ii. Dialysis modality
 - iii. (Do not exclude any patients for this analysis)
 - c. Collapse back to the facility level, and get counts and % by patient characteristic (for continuous variables like age, we use age brackets, i.e., 18-44, 45-54, 55-64, 65-74, 75+)

Patient-month level dataset / inclusion criteria

- 1) This will be a patient-month dataset
- 2) Identify all patients with at least one month of dialysis in 2017 (Jan-Dec)
- 3) Inclusion criteria
 - a. USA
 - b. Adult in the current month
 - c. Valid 2728 form (2005, 2015 form)

- d. Dialyzing in free-standing facility that has fewer than 15% pediatric
 - i. Only keep if patient can be linked to a valid facility survey and can be linked to the ownership dataset
- 4) Must have Medicare FFS in the current month of dialysis
 - a. Must have at least 12 months of Medicare FFS prior to the current month
 - b. Create indicator variable for whether the patient-month has had 36+ months of Medicare FFS
- 5) Get patient comorbidities using the CCW algorithm
 - a. Use diagnosis codes from claims in a 12 month lookback
 - b. Sensitivity analysis: use diagnosis codes from claims in a 36 month lookback
- 6) Get the zipcode of residence for that month and merge with the ACS to get zipcode characteristics
- 7) Merge with facility file to get facility characteristics + DFC outcomes (we call these facility level outcomes)
- 8) Covariates of interest:
 - a. Patient level
 - i. Age
 - ii. Sex
 - iii. Race
 - iv. Ethnicity
 - v. Whether patient had a transplant previously
 - vi. Whether the patient is incident (within the first 120 days of ESRD)
 - vii. Number of years with ESRD
 - viii. Comorbidities using CCW algorithm
 - b. Facility characteristics
 - i. Profit status
 - ii. Chain vs. independent
 - iii. Size of facility (Number of patients)
 - iv. Staff : patient ratio
 - v. ESRD Network
 - c. Zipcode Characteristics
 - i. Median income
 - ii. High school graduation rate
 - iii. % below poverty
 - d. Monthly level fixed effects (an indicator for each month of the year)
- 9) Patient Level Outcomes
 - a. Whether patient using home dialysis in the month
 - b. Whether patient was receiving dialysis optimally (defined as either peritoneal dialysis, or hemodialysis through an AV fistula or graft)
 - i. Whether patient was using a fistula
 - ii. Whether patient was using a catheter for 3+ months, including the current month (i.e., look back two months to see whether the patient used a catheter in the other two months)
 - c. Get crownweb outcomes (merge with the crownweb dataset by month/year)
 - i. Create an indicator for whether crownweb data missing for that month
 - ii. Hemoglobin < 10

- iii. Hemoglobin > 12
- iv. Calcium > 10.2
- v. Phosphorus > 7
- d. Get other outcomes
 - i. Whether patient died in that month
 - ii. Whether patient was hospitalized that month
 - iii. Whether patient had a hospitalization that month followed by a 30-day readmission
 - 1. Patients are eligible for this only if the patient was discharged alive
 - iv. Whether patient had a hospitalization that month followed by an unplanned 30-day readmission
 (<https://qualitynet.cms.gov/inpatient/measures/readmission/resources#tab3>, “2018 All-Cause Hospital Wide Measure Updates and Specifications Report Hospital-Level 30-Day Risk-Standardized Readmission Measure – Version 7.0”, pages 51 and 68)
 - v. Whether patient had a blood transfusion that month
 - 1. Criteria 1
 - a. From inpatient, outpatient, SNF claims
 - b. Revenue code 0390 OR 0392 OR 0399 PLUS any of the following HCPCS/CPT
 - i. P9010
 - ii. P9011
 - iii. P9016
 - iv. P9021
 - v. P9022
 - vi. P9038
 - vii. P9039
 - viii. P9040
 - ix. P9051
 - x. P9054
 - xi. P9056
 - xii. P9057
 - xiii. P9058
 - c. Calculate number of units of blood by taking the sum of the units for (Revenue center code 0390 OR 0392 OR 0399) across all line items that correspond to that specific day.
 - i. Sum across all days for a given month
 - 2. Criteria 2
 - a. If Criteria 1 is missing, then determine whether a blood transfusion occurred for the entire claim (assign to the month of the through date of the claim)
 - b. Look for value code 37
 - 3. Criteria 3

- a. If Criteria 1 is missing, then determine whether a blood transfusion occurred for the entire claim (assign to the month of the through date of the claim)
- b. Look for any of the following ICD procedure codes:
 - i. ICD9
 - 1. 9903
 - 2. 9904
 - ii. ICD10
 - 1. 30230H1, -P1, -N1
 - 2. 30233H1, -P1, -N1
 - 3. 30240H1, -P1, -N1
 - 4. 30243H1, -P1, -N1
 - 5. 30250H1, -P1, -N1
 - 6. 30253H1, -P1, -N1
 - 7. 30260H1, -P1, -N1
 - 8. 30263H1, -P1, -N1
- vi. Whether a patient received an ESA and their dose (using CROWNWeb data)
 - 1. Consolidate to Darbepoetin, Erythropoietin alfa, Erythropoietin beta
 - 2. Make sure units are consistent (darbe in mcg, Epo alfa in units, Epo beta in units)
 - 3. Make sure the doses are normalized, to the same mean (i.e., we want to make sure we are looking at relative changes in doses within the same ESA)
 - a. Take the mean doses of each of the ESA types, then divide all the doses by this mean. In other words, all means will be set at “1”
 - 4. For each month of dialysis create the following variables
 - a. Whether ESA administered
 - b. Type of ESA administered
 - c. Dose
 - 5. For each dialysis chain, determine the ESA that is the majority of patient-months

ANALYSES

Facility Level Outcomes

- 1) Use facility level dataset (patient level covariates are collapsed to facility level using summary statistics for that facility)
- 2) Dependent variable (left hand side)
 - a. Facility level outcomes as specified above
- 3) Independent Variables:
 - a. Whether facility is physician owned

- b. Regression 1: Control only for facility, geographic, and temporal level covariates
- c. Regression 2: Control for patient, facility, geographic, temporal level covariates.
- 4) Models: OLS for continuous outcomes, logit for binary outcomes, robust standard errors

Patient Level Regressions

- 1) Population: patient-month dataset
- 2) Dependent variable (left hand side):
 - a. Patient level outcomes
- 3) Independent variables (right hand side)
 - a. Whether patient is dialyzing in a facility that is physician owned (covariate of interest)
 - b. Covariates above (patient, facility, zipcode, temporal characteristics)
- 4) Models (in order) for all outcomes except blood transfusion and ESA outcomes:
 - a. Logit with patient level fixed effects, non-parametric bootstrap standard errors
 - b. Logit with patient level fixed effects, robust standard errors
 - c. OLS with patient level fixed effects, cluster robust standard errors at facility level
 - d. OLS with patient level fixed effects, robust standard errors
- 5) Models (in order) for whether patient received a blood transfusion
 - a. Outcomes
 - i. Criteria 1 only
 - ii. Criteria 1+2
 - iii. Criteria 1+2+3
 - b. Models
 - i. Logit with patient level fixed effects, non-parametric bootstrap standard errors
 - ii. Logit with patient level fixed effects, robust standard errors
 - iii. OLS with patient level fixed effects, cluster robust standard errors at facility level
 - iv. OLS with patient level fixed effects, robust standard errors
- 6) Models (in order) for # of units of blood transfused
 - a. Outcomes
 - i. Use the number of units of blood detected under Criteria 1. If a blood transfusion detected under Criteria 2 or 3, indicate that the patient received 1 unit of blood
 - ii. Use the number of units of blood detected under Criteria 1. If a blood transfusion detected under Criteria 2 or 3, indicate that the patient received 1 unit of blood. Also include an indicator variable that the patient had a blood transfusion detected under criteria 2 or 3.
 - iii. Use the number of units of blood detected under Criteria 1. If a blood transfusion detected under Criteria 2 or 3, indicate that the patient received 1 unit of blood. Also include an indicator variable that the patient had a blood transfusion detected under criteria 2 or 3 AND interact this indicator variable with the covariate for whether patient dialyzed in a facility that is physician owned.
 - b. Models

- i. Poisson with patient level fixed effects, non-parametric bootstrap standard errors
 - ii. Poisson with patient level fixed effects, robust standard errors
 - iii. OLS with patient level fixed effects, cluster robust standard errors at facility level
 - iv. OLS with patient level fixed effects, robust standard errors
- 7) Models (in order) for dose of ESA received
 - a. Poisson with patient level fixed effects, non-parametric bootstrap standard errors
 - b. Poisson with patient level fixed effects, robust standard errors
 - a. OLS with patient level fixed effects (dose of ESA received), cluster robust standard errors at facility level
 - i. Include covariate for chain
 - b. OLS with patient level fixed effects (dose of ESA received), robust standard errors
 - i. Include covariate for chain
 - c. Split dataset into 3 separate datasets based on CHAIN of assigned dialysis facility. Specifically, assign each chain to the type of ESA that takes up the majority of all patient-months. Separately, run the following regression on each of the datasets
 - i. Poisson with patient level fixed effects, non-parametric bootstrap standard errors
 - ii. Poisson with patient level fixed effects, robust standard errors
 - iii. OLS with patient level fixed effects (dose of ESA received), cluster robust standard errors at facility level
 - iv. OLS with patient level fixed effects (dose of ESA received), robust standard errors

Subgroup analyses

- 1) Repeat the above regressions, but this time we have the following independent variables of interest (we also include all the other adjusters)
 - a. Whether facility is physician owned (phys_own)
 - b. Whether facility is LDO owned (ldo_own)
 - c. Interaction term between these two (phys_own#ldo_own)
- 2) In addition to reporting the coefficients for these 3 terms, we also care about the following comparisons:
 - a. FOR FACILITIES THAT ARE LDO OWNED: effect of physician ownership
 - i. The parameter of interest is the sum of the following coefficients:
 $\text{phys_own} + \text{phys_own}\#\text{ldo_own}$
 - b. FOR FACILITIES THAT ARE NOT LDO OWNED: effect of physician ownership
 - i. The parameter of interest is the following coefficient: phys_own
 - c. Use the “lincom” command to estimate the sum and the standard errors of 2ai.

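### Facility patient mix: patients are assigned by plurality of 2017, but modality and dual eligibility are read in a first month that may have been at another facility

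*SAP*

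**What the plan says.** The SAP, under Analytic Datasets, Facility level dataset, step 6, builds a patient mix for each facility in three moves.

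- **Assignment (6a).** Eligible patients are adults in the USA with a valid 2728 form and at least one 2017 dialysis month that meets "Has Medicare FFS for that month of dialysis". For patients seen at more than one facility: "If a patient has multiple facilities, assign that patient to the facility that holds the plurality share". Ties are settled by 6a.iii: "If there are still ties in facilities, use the first observed facility that has the plurality".
- **Reading the characteristics (6b).** "For each patient, for the first observed month of dialysis, get" is followed by age, gender, race, ethnicity, payer, dual eligibility and dialysis modality.
- **Collapse (6c).** "Collapse back to the facility level, and get counts and % by patient characteristic".

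Under Analyses, Facility Level Outcomes, patient covariates enter as summaries of the facility. Regression 1 leaves them out. Regression 2 is described as "Control for patient, facility, geographic, temporal level covariates", without a list of which patient covariates are meant.

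**The concern.** Step 6 is meant to describe the patients each facility treats. It uses two time rules that are not connected: the facility comes from the whole of 2017, while the characteristics come from one month at the start of the patient's observation. For a patient who stays in one place the two agree. For a patient who moves early, the month that supplies modality and dual eligibility can belong to a different facility from the one credited with the patient.

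An example that follows the rules: in-center hemodialysis at facility A from January to March, then peritoneal dialysis at facility B from April to December. B holds 9 of 12 months and receives the patient. The first observed month is January at A. B's mix then counts an in-center patient, although no month at B had that modality.

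What is at stake is how well Regression 2 adjusts for patient mix. If modality or dual eligibility matters for a facility outcome and differs by ownership, an adjuster that partly describes other facilities adjusts less exactly than the plan intends.

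**Working it through.** The SAP states no figure on this point, so there is none to reproduce. The checks concern when the two rules disagree and how far a facility percentage can then be off.

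**Inputs.** From the SAP: the plurality rule (6a.ii), the tie rule (6a.iii), the first-month rule (6b) and the collapse to percentages (6c). Assumed: the plurality share is counted in months, since the SAP does not state its unit. Also assumed, because the SAP gives no rates: the share *t* of a facility's assigned patients whose first month was elsewhere, and the net share *q* of those whose recorded status differs from their status at the assigned facility.

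**Step 1: when the facilities differ.** Take *M* observed months and one move after month *k*. The second facility is assigned only if *M* − *k* > *k*, because a tie goes to the first facility.

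| Observed months *M* | Move points with a mismatch | Out of |
|---|---|---|
| 12 | *k* = 1 to 5, so 5 (45%) | 11 |
| 6 | *k* = 1 or 2, so 2 (40%) | 5 |
| 3 | *k* = 1, so 1 (50%) | 2 |
| 2 | none | 1 |

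With three different facilities in sequence over 12 months, 35 of the 55 possible splits assign the patient to a facility other than the first. These are counts of patterns, not of patients; moves need not be spread evenly over the year.

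**Step 2: which characteristics can be misrecorded.** A mismatch of facility causes an error only if the characteristic also differs.

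- Sex, race and ethnicity do not depend on the month, and an age bracket seldom changes within a year.
- Payer hardly varies if the first observed month must itself be a Medicare FFS month.
- Modality and dual eligibility can change, and modality can change together with the facility.

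**Step 3: size in a facility percentage.** Error = *t* × *q*, in percentage points:

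| *t* | *q* = 0 | *q* = 5% | *q* = 20% | *q* = 50% | *q* = 100% |
|---|---|---|---|---|---|
| 2% | 0 | 0.1 | 0.4 | 1.0 | 2.0 |
| 5% | 0 | 0.25 | 1.0 | 2.5 | 5.0 |
| 10% | 0 | 0.5 | 2.0 | 5.0 | 10.0 |
| 20% | 0 | 1.0 | 4.0 | 10.0 | 20.0 |

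For example, 0.05 × 0.20 = 0.01, or 1 point; 0.10 × 0.20 = 0.02, or 2 points. The right-hand column is the extreme in which every such patient changed status in the same direction. Because *q* is a net share, opposite changes cancel, and its sign can go either way.

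**Step 4: after the change.** If the characteristics are read in the first observed month at the assigned facility, month and facility agree by construction and the mismatch is 0.

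**Step 5: where it reaches.** Regression 1 uses no patient mix. The patient-month models take facility and outcome month by month and do not use step 6. That leaves Regression 2.

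**The case against.** The best defence is that a first-month value is a baseline measure of case mix. Home dialysis is a patient-level outcome in this study, and modality recorded later may itself be influenced by the facility. Adjusting for it could then remove part of the ownership effect. That caution is sound, and it is a reason not to replace the first-month value with the share of patient-months by modality at the facility. It does not rescue the rule as written. The SAP does not give this reason, and for patients who do not move, the first observed month is already at the assigned facility. The rule therefore mixes values from inside the facility for stayers with values from elsewhere for early movers.

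A second defence is that Regression 2 may not use modality at all. Its patient covariates are not listed, and the list of patient-level covariates for the patient-month dataset contains neither modality nor payer. This stands as a caveat: inclusion is the natural reading of step 6 together with the facility-level analysis, but it is an inference.

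The authors may also have meant the first month at the assigned facility. The text does not say so, and the proposed edit would settle it.

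A reader might infer more than the SAP supports:

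- **That the mix is wrong at every facility that receives transfers.** A transfer with no change in modality or dual eligibility causes no error, and neither does a move too late to shift the plurality.
- **That the error runs one way, under-counting home dialysis.** The SAP says nothing about the direction of switches or where they concentrate. The first observed month is the first in 2017, not the start of dialysis, and moves from home to in-center would give the opposite error.

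**Conclusion.** The point holds in a limited form. Step 6 does not tie the month in which characteristics are read to the facility credited with the patient. For early movers whose modality or dual eligibility also differs, the facility percentage can describe another facility's care.

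Size and net direction are unknown. At the assumed rates of 5% or 10% first seen elsewhere, with a net 20% of those differing, the error in a facility percentage is 1 or 2 points. Larger values need a larger share of early arrivals or a higher net switch rate, and the SAP gives neither. Nothing in it allows these errors to be turned into a shift in the ownership coefficient.

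The conclusion rests on a literal reading of 6b, on plurality being counted in months, and on the step 6 characteristics entering Regression 2. The priority is minor.

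**What to change.** Change the opening of 6b so that the characteristics are read *for the first observed month of dialysis at the assigned facility*. This gives every patient, mover or not, the same rule: status on first being observed at the facility that is credited with them. If the investigators do intend a 2017 baseline regardless of facility, the SAP should say so, give the reason and add the assigned-facility version as a sensitivity analysis.

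The cost is a few words in the SAP and one changed line in the data build. Sex, race and ethnicity keep their values, and age bracket practically so. Regression 1 and the patient-month analyses need no change.

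### The 3+ month catheter outcome (9b.ii) cannot occur in a patient's first two dialysis months, yet it is modelled on all patient-months with no at-risk rule, so the ownership estimate can be biased if new patients' moves between ownership types are unbalanced

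*SAP*

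**What the plan says.** All references are to the SAP.

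- **Outcome** (Patient-month level dataset, 9b.ii): "Whether patient was using a catheter for 3+ months, including the current month". The method is to "look back two months to see whether the patient used a catheter in the other two months". Nothing is said about months that have fewer than two earlier dialysis months.
- **Entry** (items 2 and 4a): "Identify all patients with at least one month of dialysis in 2017 (Jan-Dec"), and "Must have at least 12 months of Medicare FFS prior to the current month". The second rule concerns insurance coverage, not time on dialysis.
- **Covariates** (items 8a.vi, 8a.vii, 8d): "Whether the patient is incident (within the first 120 days of ESRD"), "Number of years with ESRD", and "Monthly level fixed effects (an indicator for each month of the year").
- **Models** (Patient Level Regressions, items 1, 3a, 4a-d): "Population: patient-month dataset". The exposure is physician ownership of the facility where the patient dialyzes. All four models, two logit and two OLS, have patient fixed effects.

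For readmission (9d.iii) the SAP does write an eligibility condition, limiting the outcome to live discharges. There is no counterpart for 9b.ii.

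**The concern.** An outcome that needs three months of history cannot be 1 in dialysis month 1 or 2, even for a patient who dialyzes only through a catheter. If those months are kept as 0, the outcome turns from 0 to 1 in month 3 simply because time has passed.

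With patient fixed effects, ownership is estimated only from patients whose ownership exposure changes. For a new catheter patient who changes ownership type in the first months, the forced zeros fall to the first type and the first possible ones to the second. If more of these moves go one way than the other, time since dialysis start is read as an ownership effect on long-term catheter use. The subgroup models with the LDO interaction repeat the same regressions and inherit the problem.

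**Working it through.** The SAP states no rate, sample size or effect for this outcome, so there is no figure of its own to reproduce.

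**1. One patient, access unchanged.** A new patient with the same catheter for 8 months scores 0, 0, 1, 1, 1, 1, 1, 1.

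| Move after month | Mean before | Mean after | Difference |
|---|---|---|---|
| 1 | 0/1 = 0.00 | 6/7 = 0.86 | 0.86 |
| 2 | 0/2 = 0.00 | 6/6 = 1.00 | 1.00 |
| 4 | 2/4 = 0.50 | 4/4 = 1.00 | 0.50 |

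Scored from month 3 only, the outcome is constant at 1. The difference is then 0, and the patient contributes nothing to a conditional fixed-effects logit. In that model this patient counts only because of the forced zeros.

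**2. Are such months in the data?** Yes, for some patients. Someone with a year of fee-for-service coverage before starting dialysis satisfies 4a in dialysis month 1. The incident covariate would serve no purpose if no such months were kept.

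**3. Do the covariates absorb the step?**

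- *Incident indicator.* 120 days is about 4 months. Over those months the patient above averages (0+0+1+1)/4 = 0.5. A single coefficient can fit that average but leaves residuals of -0.5, -0.5, +0.5, +0.5, so the step at month 3 remains.
- *Years with ESRD.* Entered as a continuous linear term, it advances equally for every patient each calendar month. Patient and month effects already span it; in a numerical check its residual was zero.
- *Month indicators.* These are calendar months, not dialysis months.

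**4. Direction.** A move into a physician-owned facility after month 2 contributes +1.00, and the reverse move -1.00. At 50:50 they cancel. At 60:40 the net imbalance is 0.60 - 0.40 = 0.20 of new patients' moves; at 70:30 it is 0.40.

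**5. Illustrative size.** These are simulations with a true ownership effect of zero, using OLS with patient and calendar-month effects and the incident indicator. All rates are assumptions. Bias is in percentage points.

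| Setting | New patients among movers | New patients' moves into physician-owned | Bias as written | Months 1-2 removed |
|---|---|---|---|---|
| A. New patients move in dialysis months 2-5 | 10 / 20 / 30% | 60% | +0.5 / +0.7 / +1.1 | 0.0 to +0.1 |
| A | 10 / 20 / 30% | 70% | +0.8 / +1.4 / +2.2 | 0.0 to +0.1 |
| B. New patients' moves spread over all observed months | 5 / 10 / 20 / 30% | 60% | 0.0 / +0.1 / +0.5 / +0.3 | not run |
| B | 5 / 10 / 20 / 30% | 70% | +0.2 / +0.3 / +0.4 / +1.1 | not run |
| C. Moves at any time | 53% | 50 / 60 / 75% | 0.0 / +0.7 / +2.2 | +0.2 / 0.0 / -0.4 |
| C. Early moves | 53% | 50 / 60 / 75% | +0.4 / +2.3 / +5.8 | +0.2 / -0.3 / -0.7 |

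Setting A has 40,000 movers, 80% of new patients starting on a catheter, 8% leaving it each month, and balanced moves among prevalent patients; the outcome mean is 16-20%. Setting B has 30,000 movers and a standard error of about 0.15. Setting C has 12,000 patients and six replicates, with 80% of new and 15% of prevalent patients starting on a catheter and monthly exit of 10% and 5%. In C, 20% of 3,000 new patients (600) and 6% of 9,000 prevalent patients (540) move, so new patients are 600/1,140 = 53% of movers, and the imbalance applies to all movers. Its standard errors as written are about 0.3 to 0.5. Its early moves take effect in dialysis month 3 or 4, the least favourable timing.

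In C, adding the incident indicator cut the bias by 17% to 38%. For example, with moves at any time and 75:25 it fell from +3.3 to +2.2.

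**The case against.** Several points on the other side are sound.

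- *Coding as 0 is not explicit.* The SAP does not say whether a month without two earlier dialysis months is 0 or missing. Zero is the literal answer to a yes/no outcome, but code could return missing. This stands; it is a reason to write the rule down.
- *Zero is the true value of the outcome as defined.* A patient in month 2 has not used a catheter for three months. That is correct, but it only renames the problem: the outcome is then tied to time since dialysis start, and the model does not adjust for that at the resolution needed.
- *The 12-month coverage rule keeps out many new patients.* Anyone whose fee-for-service coverage began at or after dialysis start has no month 1 or 2 in the dataset. This reduces the problem by an amount the SAP does not allow us to work out. It does not remove it.
- *The larger figures assume early moves or many new patients among movers.* Setting B shows that with spread-out moves and few new patients the bias is hard to tell from zero.
- *Only OLS has usable figures.* The logit models come first in the SAP's order. The mechanism applies to them, but no reliable size is available.
- *The scope is one outcome.* The optimal-dialysis and fistula outcomes (9b, 9b.i) use no look-back.

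A reader might infer more: that the second facility will appear to cause long-term catheter use, or that the ownership estimate is certain to be wrong. The SAP does not support either. It estimates an ownership effect, so moves between facilities of the same ownership type contribute nothing. Opposite moves cancel, and nothing in the SAP shows that new patients move more in one direction.

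**Conclusion.** The point holds in a conditional form. Outcome 9b.ii is impossible in dialysis months 1 and 2, no at-risk rule excludes those months, some new patients are in the dataset, and the listed covariates do not absorb the step. The ownership estimate for this outcome is therefore unbiased only if new patients' moves between ownership types are balanced, or if the code happens to set the early months to missing. The SAP secures neither.

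The size is illustrative. At 60-70% one-way moves among new patients, the false OLS effect is roughly +0.2 to +2 percentage points, with the sign reversing if the imbalance runs the other way. It is about zero at 50:50, or where few movers are new and their moves are spread out, and larger only under the early-move, high-share conditions of setting C. These sizes rest on assumed catheter rates, move timing and direction, none of which the SAP gives.

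**What to change.** Add to 9b.ii that patient-months in which the patient was not on dialysis in each of the two preceding months are set to missing for this outcome, not to 0. Run models 4a-d and the subgroup repeats for this outcome on the remaining months. The two-month check should use late-2016 records, so that prevalent patients keep January and February 2017.

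The cost is one sentence and one filter. It loses up to two months per new patient, and up to two months after any interruption of dialysis, including a return to dialysis after a transplant (8a.v keeps such patients). None of these months can show the outcome. The repair may not be complete: catheter use declines naturally after dialysis start, and with unbalanced moves a small remainder can persist (-0.4 and -0.7 points at 75:25 in setting C).

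### Death is sent to a patient-fixed-effects logit with month indicators, which has no finite estimate because death is always a patient's last record

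*SAP*

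**What the plan says.** All references are to the SAP.

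- **Data.** In the section on the patient-month level dataset, item 1 sets the unit of analysis: "This will be a patient-month dataset". Items 2 to 4 take patients with dialysis in January to December 2017 and require Medicare FFS in the current month of dialysis.
- **Outcome.** Item 9.d.i of that section is "Whether patient died in that month".
- **Time terms.** Item 8.d lists "Monthly level fixed effects (an indicator for each month of the year". Under Patient Level Regressions, item 3.b enters the "Covariates above (patient, facility, zipcode, temporal characteristics".
- **Models.** Item 4 there is headed "Models (in order) for all outcomes except blood transfusion and ESA outcomes", so it includes death. Model 4a is "Logit with patient level fixed effects, non-parametric bootstrap standard errors" and 4b is "Logit with patient level fixed effects, robust standard errors". Models 4c and 4d are OLS with patient fixed effects.
- **Subgroups.** Under Subgroup analyses, item 1 reads "Repeat the above regressions, but this time we have the following independent variables of interest": physician ownership, LDO ownership and their interaction.

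No exception, survival model or other treatment is given for death.

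**The concern.** A logit with patient fixed effects learns only from changes within a patient. That works for outcomes that can come and go, such as hospitalisation. Death happens once and ends the record, so among the patients who inform the model, calendar time alone predicts it perfectly. The month indicators carry exactly that information, and nothing is left from which to estimate the ownership effect.

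At stake is the mortality result of the two models listed first. Software may report a failure. It may instead stop somewhere on a flat surface and print an odds ratio with a credible-looking interval, and the SAP contains nothing that would alert the analyst.

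**Working it through.** The SAP gives no figure to reproduce here. The argument is algebraic; the simulations show what may be printed.

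**1. Who contributes.** Patients who do not die, or who have only one record, show no variation and drop out. A row needs a current dialysis month, so none can follow death. Every remaining patient has the sequence 0, …, 0, 1, with the 1 in the latest month T.

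**2. Likelihood.** With month coefficients g_t, ownership x_t and ownership coefficient b, each such patient contributes

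exp(g_T + b·x_T) / Σ_{t≤T} exp(g_t + b·x_t).

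**3. Separation.** Set g_t = c·t. As c grows, every contribution tends to 1 for any finite b. The log-likelihood approaches its upper limit of 0 without attaining it, and in the limit it is flat in b. Late entry and missed months do not matter, because T is still the highest month. A bootstrap resample of patients contains the same kind of sequence, so it is separated too; all 5 resamples tested were.

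**4. Size of the flatness.** Assumed, not from the SAP: 100,000 patients, 12 months, 1.4% monthly death risk, 25% starting in a physician-owned facility, 2% per month switching in and 1% out, one dataset per scenario. Then 85,704 patients drop out and 14,296 decedents remain. At c = 20 each contributes a log-likelihood of about −e^(−20) = −2.06 × 10⁻⁹, and 14,296 × 2.06 × 10⁻⁹ ≈ 0.00003. The computed value is −0.00003 at b = −2, 0 and +2 alike.

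**5. Separation test.** In a smaller simulation (6,000 patients, 908 deaths, 805 informative), a linear programme found complete separation, also with b fixed at +5 or at −5. The Newton fit ran as follows:

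| Iteration | Log-likelihood | December minus January | Model-based SE of b |
|---|---|---|---|
| 0 | −1394 | 0 | 0.27 |
| 5 | −15.8 | 49 | 2.0 |
| 12 | −0.015 | 126 | 67 |
| 24 | −9 × 10⁻⁸ | 258 | 26,868 |

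**6. Why 4b hides this.** At month slope c the information is of order e^(−c), so the model-based SE grows as e^(c/2). Late Newton steps raise the December-January gap by 11, that is c by 1 per month. Four steps should then multiply the SE by e² = 7.39; from iteration 12 to 16 it went from 66.6 to 492.1, a ratio of 7.39. The sandwich has squared scores of order e^(−2c) in the middle and two inverse informations of order e^(c) outside, so the growth cancels. In the larger simulation with no true effect, the model-based SE was 0.46, 5.5 and 24.8 after 5, 10 and 13 iterations, while the robust SE stayed at 0.075.

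**7. What would be printed.** The true effects are risk differences of ±0.7 points on 1.4%: (0.021/0.979)/(0.014/0.986) = 1.51 and (0.007/0.993)/(0.014/0.986) = 0.50.

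| True OR | Newton from zero stops at | Robust 95% CI |
|---|---|---|
| 1.51 | 1.12 | 0.99 to 1.27 |
| 0.50 | 1.03 | 0.85 to 1.26 |

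Both intervals exclude the truth. With no true effect, Newton stopped at 1.07 to 1.29 depending on the start value, and quasi-Newton optimisers at 7 to 374.

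**8. Subgroup repeats.** Adding LDO ownership and the interaction leaves the separating month direction in place. At c = 20 the log-likelihood was −0.00003 to −0.00005 at five very different sets of the three coefficients, so the lincom sum is undetermined as well.

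**9. Models 4c and 4d.** Fixed-effects OLS is finite. With 150,000 patients and 6 replicates, the null coefficient lay within 0.07 percentage points of zero in all 20 scenarios. The share of a true 0.70-point difference recovered ran from 64% to 114%, depending on the assumed starting ownership share and switching.

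**10. Dropping the month indicators.** The logit then converges, but because death is always last the estimate follows the direction of switching. In the 6,000-patient data, with a true coefficient of 0.2 (OR e^0.2 = 1.22), it gave 1.386 (SE 0.295), an OR of 4.0. Across switching patterns, null ORs ran from 1.04 to 8.3.

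**The case against.** - **One calendar year.** The proof needs all rows to lie within one year. Item 2 literally selects patients, and no item separately drops rows outside 2017. In 24-month simulated data with month-of-year indicators alone, the separation disappeared. This condition should be stated, but it is the natural reading given January to December 2017, 2017 facility files and month-of-year indicators. In longer data, age or years with ESRD measured finely enough to rise each month would restore the separation.
- **Ordered models.** If the order is a fallback sequence, mortality would move to the computable OLS models. The SAP does not say so and gives no convergence rule, and 4b may print a plausible result that triggers no fallback. OLS can also misstate the size of a real effect.
- **Illustrative figures.** The printed odds ratios come from one dataset per scenario, and the software's optimiser and stopping rule are unknown. This stands: they do not predict what the study would see. The pattern does repeat. Other runs stopped at 1.02, 1.06 and 1.07 for a true OR of about 1.5, and at 0.95, 0.96 and 0.99 for a true OR of about 0.5.
- **Changed estimand.** A pooled model gives up the within-patient comparison chosen for the patient-level outcomes. That is a real cost and must be declared, but the fixed-effects logit cannot deliver that comparison for a terminal event.
- **Limited reach.** Death is one outcome among many and is not labelled primary in this SAP. Hospitalisation and other repeatable outcomes are untouched by this argument.

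**Conclusion.** The concern holds. For death, models 4a and 4b and their subgroup versions have no finite maximum-likelihood estimate, and neither choice of standard error repairs this. The result needs only that rows fall within one calendar year and that month indicators are in the model; it does not depend on assumed rates. The assumed rates matter only for the illustration: an arbitrary odds ratio, near 1 when Newton starts from zero, with a robust interval that can exclude true values of 1.51 or 0.50. Models 4c and 4d are computable and near zero under no effect, but are not a dependable measure of the size of an effect. This must be corrected before mortality is analysed.

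**What to change.** Take death out of item 4 under Patient Level Regressions and give it its own item:

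- a discrete-time hazard model, by pooled logit or complementary log-log, on the same patient-month rows;
- no patient fixed effects;
- month indicators and all listed patient, facility and zipcode covariates;
- standard errors clustered by facility.

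Make the same change for death in the subgroup interaction models, including the lincom sum. State that rows are limited to 2017, and that the mortality estimate is a between-patient comparison relying on the measured covariates.

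In the same simulations the pooled logit with month indicators gave ORs of 0.99 to 1.01, 1.50 to 1.53 and 0.49 to 0.50 for true values of 1.00, 1.51 and 0.50. No confounding was built in, so this shows that the effect can be estimated, not that confounding is controlled.

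The cost is SAP wording and a few model commands, with no new data. What is given up is within-patient control of unmeasured stable differences.
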